7.4.2.5 Dose Reductions/Escalation

There will be no dose escalations or reductions of nivolumab allowed.

7.4.3 Concomitant Medications

Concomitant medications, defined as medications other than study medications which are taken at any time on-treatment (i.e. on or after the first day of study therapy and within 100 days following the last dose of study therapy), will be coded using the WHO Drug Dictionary.

The following summary tables by treatment group will be provided:

- Concomitant medications (subjects with any concomitant medication, subjects by medication class and generic term).

A by-subject listing will accompany the table.

[REDACTED]

[REDACTED]

[Redacted]

[Redacted]

- [Redacted]
- [Redacted]
- [Redacted]
- [Redacted]
- [Redacted]

[Redacted]

[Redacted]

- [Redacted]

[Redacted]

[Redacted]

7.4.3.3 Subsequent Cancer Therapy

Number and percentage of subjects receiving subsequent cancer therapies will be summarized. Categories include:

- Subsequent systemic therapy
- Subsequent surgery for treatment of tumors (restricted to tumor resection)
- Subsequent radiotherapy for treatment of tumors

A by-subject listing of subsequent cancer therapy will also be produced for all randomized subjects.

7.5 Efficacy

Unless otherwise specified, the primary population will consist in the all randomized subjects and the analysis will be performed by treatment group as “randomized”.

Unless stated otherwise, whenever a stratified analysis is specified, the following stratification factors (recorded at randomization as per IRT) will be used:

- Extent of tumor resection (complete or partial)

7.5.1 Overall Survival

7.5.1.1 Primary Analysis

The primary objective of the study is to compare the overall survival between treatment groups in all randomized subjects.

Overall survival will be compared between the treatment groups using stratified log-rank test (5% alpha level), the two-sided log-rank p-value will be reported. The stratified hazard ratio between the treatment groups will be presented along with the 95% CI.

OS will be estimated using the KM techniques. A two-sided 95% CI for median OS in each treatment group will be computed via the log-log transformation method. OS rates at fixed time points (e.g. 12, 18, 24 months, depending on the minimum follow-up) will be presented along with their associated 95% CIs. These estimates will be derived from the Kaplan Meier estimate and corresponding CIs will be derived based on Greenwood formula for variance derivation and on log-log transformation applied on the survivor function. Minimum follow-up must be longer than the timepoint to generate the estimate. In case the minimum follow-up is less than the timepoint, but it is judged that data immaturity does not affect interpretability of the results, the estimate will be provided.

The status of subjects who are censored in the OS KM analysis will be tabulated for each treatment group using the following categories:

- On-study (on-treatment, in follow-up)
- Off-study (lost to follow-up, withdraw consent, never treated)

To examine the assumption of proportional hazards in the Cox regression model, in addition to treatment, a time-dependent variable defined by treatment by time interaction will be added into the model. A two-sided Wald Chi-Square p-values of less than 0.1 will indicate a potential nonconstant treatment effect. In that case, additional exploratory analyses may be performed.

A by-subject listing will be presented including treatment arm, OS, whether the subject was censored, and if censored, the subject’s status.

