Sample Size: Approximately 550 subjects will be randomized to the two arms (RT + nivolumab vs RT + TMZ) in a 1:1 ratio, stratified by complete or partial resection at baseline.

This study requires at least 390 events (ie, death) to provide 90% power to detect a hazard ratio (HR) of 0.72 with an overall type 1 error of 0.05 (two-sided). This translates to an observed HR of 0.82 (median OS of 13.0 vs 15.8 months) or less resulting in a statistically significant improvement.

The secondary endpoint of only PFS will be tested hierarchically.

Endpoints: The primary endpoint is OS. OS is defined as the time between the date of randomization and the date of death due to any cause. A subject who has not died will be censored at the last known alive date. OS will be followed continuously while subjects are on study drug and every 3 months (± 14 days) via in-person or phone contact during survival follow-up phase of the study.

The secondary endpoint of PFS is defined as the time from randomization to the date of the first documented tumor progression or death due to any cause. Subjects who die without a reported progression will be considered to have progressed on the date of death. Subjects who did not have disease progression or die will be censored at the date of last tumor assessment. Subjects who did not have any on study tumor assessment and did not die will be censored at the randomization date. Subjects who started any subsequent anti-cancer therapy without a prior reported progression will be censored at the last tumor assessment prior to initiation of the subsequent anti-cancer therapy. Subjects who had surgical resection post start of study treatment will be censored at the last tumor assessment date prior to initiation of surgical resection. PFS will be determined by investigator reported response based on RANO criteria

The secondary endpoint of survival rate at 24 months, is defined as Kaplan-Meier survival probability at 24 months.

An additional secondary endpoint is OS and PFS assessed in the TMB-high population, as assessed in the TMB assay where the numerical cut-off for high versus low will be specified in the statistical analysis plan. Definition for OS and PFS for this endpoint will be the same as defined earlier.

Analyses:

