The analyses of primary endpoint of OS and secondary endpoints of PFS and OS[24] will be based on all randomized subjects. If superiority in OS is demonstrated, a hierarchical hypothesis testing approach for the secondary endpoint of PFS will be used to preserve a study-wise type I error rate at 0.05. OS[24] will be estimated using Kaplan Meier method. OS and PFS will also be estimated for the TMB-high population.

OS and PFS distribution in all randomized subjects will be compared between treatment groups using a two-sided stratified log-rank test. The hazard ratio (HR) and corresponding two-sided 95% confidence intervals (CIs) will be estimated in a Cox proportional hazard model using treatment as a single covariate stratified by complete or partial resection at baseline.

OS and PFS curves will be estimated using the Kaplan- Meier product-limit method. Median OS and PFS along with the corresponding two-sided 95% CIs using the log-log transformation will be computed.

OS [24] and the corresponding 95% CIs using the log-log transformation will be computed after all subjects have follow-up of at least 24 months. OS and PFS in the TMB-high population will be estimated using the Kaplan-Meier method.

TABLE OF CONTENTS

TITLE PAGE 1

DOCUMENT HISTORY 3

OVERALL RATIONALE FOR THE REVISED PROTOCOL 05 6

SUMMARY OF KEY CHANGES OF REVISED PROTOCOL 05..... 6

SYNOPSIS..... 9

TABLE OF CONTENTS..... 13

[REDACTED] 17

[REDACTED] 18

[REDACTED] 18

[REDACTED] 19

[REDACTED] 20

[REDACTED] 20

[REDACTED] 22

[REDACTED] 22

[REDACTED] 23

[REDACTED] 23

[REDACTED] 23

[REDACTED] 24

[REDACTED] 25

[REDACTED] 25

1.2 Research Hypothesis 25

1.3 Objectives(s) 25

 1.3.1 Primary Objective 25

 1.3.2 Secondary Objectives 25

 1.3.3 Exploratory Objectives 25

[REDACTED] 26

[REDACTED] 26

[REDACTED] 27

[REDACTED] 28

[REDACTED] 28

[REDACTED] 29

2 ETHICAL CONSIDERATIONS 29

 2.1 Good Clinical Practice 29

 2.2 Institutional Review Board/Independent Ethics Committee 30

 2.3 Informed Consent 30

3 INVESTIGATIONAL PLAN 31

 3.1 Study Design and Duration 31

 3.1.1 Screening Phase 33

 3.1.2 Treatment Phase 35

 3.1.2.1 Randomization and Initiation of Treatment 35

 3.1.2.2 Radiotherapy 35

[figure not shown]
[figure not shown]
[figure not shown]
[figure not shown]
[figure not shown]
[figure not shown]

[figure not shown]
[figure not shown]
[figure not shown]
[figure not shown]
 3.1.3 Follow-up Phases 36

 3.1.4 Overall Study Duration 36

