5 STUDY ASSESSMENTS AND PROCEDURES

5.1 Flow Chart/Time and Events Schedule

Table 5.1-1: Screening Procedures (CA209498)		
Procedure	Screening Visit 1	Notes
Informed Consent for Enrollment	X	Call IVRS to obtain subject number; see Section 3.1.1
Inclusion/Exclusion Criteria	X	Must be confirmed prior to randomization
Medical History	X	
Physical Examination, Vital Signs, Performance Status	X	Height, weight, BSA; Karnofsky performance status (Appendix 3), and full physical exam, BP, HR, RR, temperature, within 14 days prior to randomization
Tumor Sample Submission	X	Surgical biopsy (block or slides) Submission: See Laboratory Manual. Central Laboratory MGMT result must be available prior to randomization.
Baseline Tumor Assessment	X	Contrast-enhanced MRI ^a within 72 hours post-surgery (within 24 hours preferred); (see Imaging Manual). If not available, must be performed prior to randomization (> 2 weeks post-op preferred). See Section 5.4 .
Assessment of Signs and Symptoms	X	Within 14 days prior to randomization
Concomitant Medication collection	X	Within 14 days prior to randomization, to include corticosteroid dose
Adverse Events Assessment	X	Serious Adverse Events from time of consent. See Section 6.1.1
Laboratory Tests	X	CBC w/differential; Chemistry panel including: AST, ALT, ALP, T.Bili, BUN or serum urea level, albumin, creatinine, phosphorus, Ca, Na, K, Cl, LDH, Glucose, within 14 days prior to randomization. TSH, T3 and T4 (Free or Total), Hep B/C (HBVsAG, HCV antibody or HCV RNA), within 28 days prior to randomization
Urinalysis	X	Dipstick, obtain within 14 days prior to randomization
Pregnancy Test [WOCBP only]	X	Serum or urine pregnancy test (minimum sensitivity 25 IU/L or equivalent units of HCG) to be done at screening visit and within 24 hours of first dose of study therapy

- ^a Post-operative baseline MRI following consensus recommendations must be obtained prior to randomization. It is strongly recommended that this scan be obtained <72 hrs or >14 days post-surgery in order to minimize artifact. There is no requirement that MRI performed prior to randomization be on a “qualified machine.” See [section 5.4](#)

Table 5.1-2: On-Treatment Assessments (CA209498)

Procedure	RT + TMZ	TMZ Maintenance	RT + Nivolumab	Notes: Windows refer to calendar days. Procedures must be done within 72h prior to dosing unless otherwise specified.
IVRS Randomization call	Day 1		Day 1	Confirm eligibility criteria prior to randomization.

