7 DATA MONITORING COMMITTEE AND OTHER EXTERNAL COMMITTEES

When required, adjudicated events will be submitted to the DMC and Health Authorities for review on a specified timeframe in accordance with the adjudication documentation.

A Data Monitoring Committee will be established to provide oversight of safety and efficacy evaluation of the entire study and to provide advice to the sponsor regarding actions the committee deems necessary for the continuing protection of subjects. The DMC will be charged with assessing such actions in light of an acceptable benefit/risk profile for nivolumab. The DMC will act in an advisory capacity to BMS and will monitor subject safety and evaluate the available efficacy data for the study. The oncology therapeutic area of BMS has primary responsibility for design and conduct of the study. The DMC will meet at least every 6 months or more frequently as needed on an ad-hoc basis. Information regarding DMC membership, responsibilities, and procedures are detailed in the DMC charter. The DMC will be informed should a safety signal emerge and may convene an ad-hoc meeting on its own initiative. The DMC will review all available data (safety and efficacy) at each meeting. At the conclusion of each DMC meeting, the committee will provide the sponsor with a recommendation to continue, modify, or terminate the study protocol based upon their review. Ultimately, decisions regarding the study protocol will be made by the sponsor in conjunction with feedback from investigators and the DMC.

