8.4.2.1 Analyses of Primary Endpoint

The distribution of OS in all randomized subjects will be compared in arms RT + nivolumab and RT + TMZ at the final analysis via a two-sided, log-rank test, stratified by complete resection or partial resection at baseline. The Kaplan-Meier product limit method will be used to estimate the survival curve in each arm including medians and its 95% CI, OS rates at pre-specified time points. The HR and the corresponding two-sided 95% CIs will be estimated in a Cox proportional hazards model with treatment arm as a single covariate stratified by corresponding stratification factor (complete or partial surgical resection at baseline).

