5 SAMPLE SIZE AND POWER

This is a Phase 3, randomized, open label, multicenter study of RT + nivolumab versus RT + TMZ in adult (≥ 18 years) subjects with newly diagnosed GBM subjects with unmethylated MGMT tumors.

Primary objective of the study is to compare the overall survival (OS) of RT+ nivolumab versus RT+TMZ in subjects with newly diagnosed GBM subjects with unmethylated MGMT tumors after surgery.

The sample size for this study is based on the following assumptions:

- 1) OS follows exponential distribution
- 2) Median OS in RT + TMZ arm is 13.0 months (Weller 2009⁵)
- 3) Hazard ratio (HR) of arm RT + nivolumab vs. RT + TMZ is 0.72, translated to median OS improvement of 5.0 months (13.0 months vs. 18.0 months for arm RT + TMZ and arm RT + nivolumab, respectively)

At least 390 events (i.e., death) provide 90% power to detect a hazard ration (HR) of 0.72 with an overall type 1 error of 0.05 (two-sided). This translates to an observed HR of 0.82 (median OS of 13.0 vs. 15.8 months) or less resulting in a statistically significant improvement.

Approximately 550 subjects will be randomized to the two arms (RT +nivolumab vs. RT + TMZ) in a 1:1 ratio stratified by complete or partial resection at baseline. Accrual will take approximately 10 months. The total duration of the study from start of randomization to final analysis of OS is expected to be approximately 33 months (10 months of accrual + 23 months of follow-up (Table 5-1)

Power calculations were done using East v 6.3.

Table 5-1: Key Parameters of Sample Size calculation

Assumptions	Analysis	Goal/Timing (from first subject randomized)	Significant Nominal p-value	Probability for declaring superiority Under HA/H0
$\alpha = 0.05$	Final	390	Superiority Observed nominal	90%/ 5%

Table 5-1: Key Parameters of Sample Size calculation

[figure not shown]

Assumptions	Analysis	Goal/Timing (from first subject randomized)	Significant Nominal p-value	Probability for declaring superiority Under HA/H0
Power = 90%	Superiority	OS events/ 33 months	p-value ≤ 0.05	
Control arm (RT+TMZ) median OS = 13.0 months;			No Superiority nominal p-value > 0.05	
Treatment arm (RT + Nivolumab) Median OS = 18.0 months HR = 0.72				

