7.5.3 Progression Free Survival

7.5.3.1 Primary Analysis

The PFS curves for each treatment group will be estimated using the Kaplan-Meier (KM) product-limit method. Median PFS and the corresponding two-sided 95% confidence intervals using the log-log transformation will be computed.

PFS will be compared between the two randomized arms using two-sided (5% alpha level) stratified log-rank test. This comparison will only be tested if OS comparison is positive.

In addition, a stratified Cox proportional hazards regression model will be used to estimate hazard ratio between treatment groups along with the 95% CI.

PFS rates at 6, 9, 12, and 18 months will be estimated using KM estimates on the PFS curve for each treatment group. Minimum follow-up must be longer than the time point to generate the rate. The associated two-sided 95% CI will also be calculated.

The source of progression (death vs. progression) will be summarized by treatment group.

The status of subjects who are censored in the PFS KM analysis will be tabulated for each treatment group using the following categories:

- On-study (on-treatment, in follow-up)
- Off-study (lost to follow-up, withdrawn consent, never treated)
- No baseline tumor assessment
- No on-study tumor assessment and no death

- Received subsequent anti-cancer therapy

[figure not shown]
A by-subject listing will be presented including treatment arm, PFS, whether the subject was censored, and if censored, the subject’s status.

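### The primary OS test is valid and has its stated 90% power, but it leaves out age and Karnofsky status; prespecified adjustment would add about 0 to 1.7 power points under assumed none-to-moderate prognostic effects

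*SAP*

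**What the plan says.** **The test.** SAP 7.5.1.1 sets the primary analysis: "Overall survival will be compared between the treatment groups using stratified log-rank test (5% alpha level". The test is two-sided. The protocol synopsis agrees: "OS and PFS distribution in all randomized subjects will be compared between treatment groups using a two-sided stratified log-rank test". SAP 7.5 names extent of resection as the only factor for stratified analyses, as recorded at randomization. Protocol 8.4.2.1 takes the hazard ratio from a "Cox proportional hazards model with treatment arm as a single covariate stratified by corresponding stratification factor".

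**Age and KPS.** Protocol 4.4 and SAP 2.2 require date of birth for the randomization call. Protocol Table 5.1-1 schedules "Karnofsky performance status (Appendix 3), and full physical exam, BP, HR, RR, temperature, within 14 days prior to randomization", and Protocol 3.3.1 uses KPS ≥70 as an entry criterion. For OS, the two variables appear only in SAP 7.5.1.2 item 4 (a Cox model with age, steroid use and KPS, with backward elimination at 0.15) and in the subgroup plots of SAP 7.5.1.3.

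**Design figures.** SAP 5 states: "Hazard ratio (HR) of arm RT + nivolumab vs. RT + TMZ is 0.72, translated to median OS improvement of 5.0 months". The protocol synopsis adds the significance threshold: "This translates to an observed HR of 0.82 (median OS of 13.0 vs 15.8 months) or less". There is no interim analysis, and PFS depends on the OS result: "This comparison will only be tested if OS comparison is positive".

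**The concern.** One OS test at 390 deaths decides both confirmatory claims, because PFS is tested only after OS. If age and KPS predict survival in this population, a test that ignores them gives up some power that the same deaths could supply. The sponsor evidently regards them as potentially prognostic, since it chose them for the sensitivity model. That model adds nothing to the confirmatory test, and its covariates are selected from the data. Both variables are already collected, so using them needs no new data.

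**Working it through.** **1. Reproduce the plan.** Inputs from SAP 5: HR 0.72, two-sided alpha 0.05, 90% power, 1:1 allocation.

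- Deaths = 4(1.960 + 1.282)² / (ln 0.72)² = 389.5, so 390. This matches.
- Standardised effect at 390 deaths = (√390 / 2) × 0.3285 = 3.244. Power = Φ(3.244 − 1.960) = 90.04%. This matches.
- Critical HR = exp(−2 × 1.960 / √390) = 0.820. This matches.

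**2. The adjusted test.** Each subject's contribution to the stratified log-rank numerator (the derived outcome) is regressed linearly on age and KPS, by arm and centred within resection stratum. The fitted imbalance is subtracted from the numerator, and the variance is reduced to match. The null hypothesis is unchanged.

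**3. Assumptions not in the documents.** KPS ≤80 in 35% of subjects; resection split 50:50; steroid users 40%; independent covariates; permuted blocks of 4. Survival is exponential given covariates, with a marginal control median of 13 months. The 550 subjects accrue uniformly over 10 months, and the data are cut at the 390th death. The treatment effect was tuned so that the stratified HR averages 0.72, because the plan ties 0.72 to arm medians of 13 and 18 months.

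**4. Simulation.** 20,000 trials per scenario under HR 0.72 and 20,000 under the null.

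| | None | Weak | Moderate | Strong |
|---|---|---|---|---|
| Age HR per SD | 1.00 | 1.15 | 1.30 | 1.50 |
| KPS ≤80 HR | 1.00 | 1.25 | 1.50 | 2.00 |
| Resection HR | 1.2 | 1.2 | 1.4 | 1.6 |
| Steroid HR | 1.1 | 1.1 | 1.2 | 1.4 |
| Power, current test (%) | 90.1 | 90.1 | 90.2 | 90.1 |
| Power, adjusted (%) | 90.1 | 90.6 | 91.9 | 94.2 |
| Paired gain (points) | 0.06 | 0.47 | 1.70 | 4.14 |
| SE of gain | 0.06 | 0.10 | 0.14 | 0.16 |
| Type I error, current (%) | 5.2 | 5.2 | 4.9 | 5.0 |
| Type I error, adjusted (%) | 5.2 | 5.1 | 5.1 | 5.3 |
| Variance ratio, adjusted to current | 0.996 | 0.976 | 0.932 | 0.855 |
| Mean month of 390th death | 32.6 | 32.9 | 33.9 | 36.0 |

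The SE of each type I error figure is 0.15 points.

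**5. Formula check on the gains.** Power ≈ Φ(3.244 / √ratio − 1.960), which gives 90.2 / 90.7 / 91.9 / 93.9%. These are gains of about 0.1 / 0.7 / 1.9 / 3.9 points, in line with the simulation. As an equivalent number of deaths, 390 / ratio − 390 gives about 2 / 10 / 28 / 66.

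**6. A different adjusted test.** A stratified Cox Wald test with age and KPS was simulated with somewhat different strengths (age 1.00 / 1.15 / 1.25 / 1.45; KPS 1.0 / 1.2 / 1.4 / 1.7 in 40%; 24,000 trials each). It gave −0.1 / +0.6 / +1.8 / +4.5 points.

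**7. Agreement of p-value and interval.** The adjusted p-value disagrees with the existing stratified 95% CI in 0.7 / 2.0 / 3.7 / 5.6% of trials, against 0.04–0.06% under the current plan. A matching HR, from the stratified Cox score equation with the same covariate correction, also averages 0.72. It disagrees with the adjusted p-value in only 0.04–0.05% of trials.

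**8. Why one test must be named.** Under the null, taking whichever of the two tests is significant rejects in 5.4 / 5.9 / 6.2 / 7.0% of trials.

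**The case against.** The strongest reply is that nothing is broken. The planned test uses the randomization factor, controls alpha and delivers its stated power, and choosing another valid test is a matter of preference. The gain is wholly assumed and may be nil. Eligibility may narrow both covariates (KPS ≥70; subjects unsuitable for full-dose radiotherapy excluded). SAP 3.0 is dated 15-Jan-2019 and already refers to the primary lock, and the trial is open-label, so changing the primary test late invites challenge. A small share of trials (0.3–1.0%) would have a stratified CI excluding 1 while the adjusted test is not significant.

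All of this stands, and it limits the weight of the point. It does not remove the case for a cheap, prespecified use of data already collected, and the fallback below meets the timing objection.

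Three stronger readings are tempting, and the documents do not support them:

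- *The trial is underpowered.* If 0.72 were the HR conditional on age and KPS, log-rank power in the Cox simulation of step 6 would be 88.7 / 87.4 / 83.3% (weak / moderate / strong). But the plan derives 0.72 from arm medians, so it is not that conditional HR.
- *A gain of about 4 points should be expected.* The strong case fits the plan's own timing worst: the 390th death falls at 36.0 months against 33.
- *Sensitivity analysis 4 is itself defective.* A reader might think that steroid use is undefined, that stratification is unstated, or that elimination conflicts with reporting an HR for each covariate. The steroid definition may lie in redacted text, SAP 10 says that the model is stratified by IVRS resection, and each covariate can mean each one retained.

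**Conclusion.** The point holds as an efficiency option, at the level of something to consider. The current primary test is valid and has 90% power at 390 deaths. Adjusting for age and KPS adds about 0 / 0.5 / 1.7 points under assumed none / weak / moderate effects, with type I error near 5%. About 4 points is an upper scenario that sits poorly with the planned 33 months. The sizes rest on the assumed prognostic strengths and covariate frequencies, none of which the documents give, and on reading 0.72 as the stratified HR without age and KPS. Confidence is medium.

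**What to change.** **If it can be documented, before database lock, that the change is made without access to OS by arm**, amend Protocol 8.4.2.1, the synopsis (for OS only) and SAP 7.5.1.1. The DMC should take no part, since "The DMC will review all available data (safety and efficacy) at each meeting". Suggested wording:

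> OS will be compared with a two-sided 5% covariate-adjusted log-rank test, stratified by resection per IVRS and adjusted for age (continuous) and KPS (≤80, >80; last value on or before randomization). Derived outcomes are regressed on these covariates by arm, centred within stratum. Missing KPS is assigned to the more frequent category, pooled over arms.

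Then:

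- keep the current stratified log-rank test as the first sensitivity analysis;
- report the matching covariate-adjusted HR and CI beside the stratified HR, and say that the stratified CI may not agree with the adjusted p-value;
- note in the synopsis, Protocol 8.1 and SAP 5 that the observed-HR threshold of 0.82 is approximate.

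**If that documentation is not possible**, keep the current primary test and add the adjusted test as the first prespecified supportive analysis, with age and KPS forced in.

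**Cost.** The first route needs a short protocol amendment and SAP wording. It changes the test that gates PFS, and it brings the p-value and CI disagreement shown above, which the matching HR all but removes. The fallback needs SAP wording only.
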